16.2.6.3 Other safety measures

Vital signs at each planned assessment, and change in vital signs from baseline at each planned post-baseline assessment, will be summarised by actual treatment.

Vital signs of potential clinical importance will be listed separately.

QT interval will be corrected using Fridericia's (QTcF) formulae.

ECG variables will be summarised by treatment and timepoint. Differences from baseline will be summarised by treatment and timepoint.

QTcF > 450 msec and increases in QTcF from baseline (Day 1 predose) of > 30 msec will be considered to be potentially clinically important. The number of subjects with a potentially clinically important QTcF will be summarised by actual treatment and timepoint, giving the numbers of subjects with QTcF > 450 msec, > 480 msec and > 500 msec, and the numbers of subjects with increases in QTcF from baseline of > 30 msec and > 60 msec⁴⁰. A supporting listing of all subjects with a QTcF value of potential clinical importance, and a separate listing of ECG findings classified as abnormal by the investigator, will also be provided.

Abnormal physical examination findings will be listed.

Positive C-SSRS data will be listed (Part C only).

16.2.7 Pharmacokinetic data analyses

PK concentration data will be summarised using the PK concentration population. PK parameters will be summarised using the PK parameter population.

For log-transformed parameters, the primary measure of central tendency will be the geometric mean⁴¹; for untransformed parameters, it will be the arithmetic mean or median.

For all variables, N (number of subjects in receiving the treatment/formulation in the population), n (number of observations), arithmetic mean, median, minimum, maximum, SD, %CV (coefficient of variation), and the 95% CI of the arithmetic mean will be derived. For log-transformed variables, all of the above plus the geometric mean, its 95% CI, and the SD of the log-transformed variables, will be provided.

Plasma concentrations and PK parameters will be listed and summarised, by treatment, using descriptive statistics. Individual and mean plasma concentration–time profiles will be presented graphically. All available data will be used to derive PK parameters in individual subjects.

In Parts B and C, urine concentrations, and urine PK parameters will be listed and summarised, by treatment, using descriptive statistics.

Food effect analysis

To assess the effect of food in Part B, analysis of variance (ANOVA) models will be fitted with the logarithm of the PK parameters (AUC_{inf} , AUC_{last} and C_{max}) as the dependent variables, and formulation as a fixed effect. The estimated least square means and residual variance from the model will be used to construct 90% CIs for the difference in means on the log scale for the comparison of fed versus fasted solutions. Food effect will be concluded if the 90% CI of the ratio (fed:fasted) is not included within the range 80–125%.

For t_{max} , the Hodges Lehmann estimator of the difference between fed and fasted solutions in median values and the 90% CI generated with the Moses method will be presented.

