2.4 Type of trial

This is a Phase 1, single-centre trial to assess the safety, tolerability, PK and food effect of BEN8744 in healthy volunteers.

This trial will be in 3 parts, as follows:

Part A will test single doses of BEN8744 in a double-blind, randomised, placebo-controlled and dose-escalating design.

Part B will test the effect of food on the PK of BEN8744 in an open-label, randomised, 2-way crossover design.

Part C will test repeated doses of BEN8744 (once or twice daily for 14 days) in a double-blind, randomised, placebo-controlled and dose-escalating design.

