After single doses of 2–60 mg, BEN8744 demonstrated a shorter than expected elimination half-life, ranging approximately 2–4 h. At the highest dose tested (60 mg), mean C_{avg} was below IC_{90} . However, a single subject had a higher AUC_{inf} , approximately 2-fold above the mean and above IC_{90} . In all subjects after 60 mg BEN8744, plasma concentrations decreased below the IC_{50} by 11 h postdose. Considering the observed short half-life, and predicted required time above IC_{50} for efficacy in patients, a twice daily dosage regimen will be required in Part C (MAD Phase) to achieve exposures above IC_{50} for up to 18–24 h.

The impact of gut P-glycoprotein (P-gp) efflux and gut cytochrome p450 3A4 (CYP3A4) mediated metabolism was not expected to be significant in humans; however, emerging clinical data suggests there is an impact which is significant at lower doses. Between 2 and 6 mg QD the increase in PK parameters appeared dose-proportional, but escalation between 6, 20 and 60 mg QD resulted in a greater than proportional increase in AUC_{inf} , suggestive of non-linear PK. Additionally, between-subject variation was high. While the linear approach overpredicted exposures at low doses, the mean C_{max} and AUC_{inf} at 60 mg aligns with predicted exposures. Mean apparent clearance (CL/F) decreased with an increase in dose from 6 to 60 mg QD, which may indicate approaching saturation of gut P-gp and CYP3A4. Hence, at higher doses exposure is expected to be closer to dose-proportional.

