8.1.2 Part B

Enrolment of up to 12 healthy subjects is planned, in up to 2 groups (Groups B1 and B2).

Each subject in Part B will have 2 study sessions (Sessions 1 and 2), in which they will receive a single dose of BEN8744, by mouth. Each subject will receive BEN8744 after an overnight fast of at least 10 h in one session, and after an FDA high-fat breakfast (1,013 kcal, 59.2 g fat [of which 28.1 g saturated fat]) in the other session; the order will be randomised 1:1, as shown in Table 7. A subject's doses

will be separated by a washout of at least 7 days (or 5 half-lives as determined in Part A, whichever is longer). Subjects dosed on the same day may be dosed at intervals of at least 10 min.

Table 7 Treatment sequence for each group (n=6 each) in Part B

	Session 1	Session 2
n=3 subjects	Fed	Fasted
n=3 subjects	Fasted	Fed

The dose to be tested in Group B1 will be decided following review of the interim safety, tolerability, and PK data from at least 3 dose levels in Part A, as described in section 8.5.3.

To reduce the risk of unexpectedly high plasma concentrations, the dose selected for Group B1 will be no higher than 50% of the highest dose tested in Part A that caused no safety concerns.

Group B2 is optional and may be required if the Sponsor decides to test the effect of food at an additional dose level (for example, if absorption and hence exposure is not proportional to dose in Part A) or under different conditions (eg with different fasting requirements or after a different meal such as a standard breakfast). The dose and food requirements for Group B2 will be decided following review of the interim safety, tolerability, and PK data from Group B1 and all available data from Part A.

Subjects will be screened within 28 days before their first dose of trial medication. Subjects will be resident on ward from 1 day before their dose (Day -1) until up to 72 h after dosing (Day 4). They will return for a follow-up visit 7 (± 2) days after their inpatient stay in Session 2 (Day 11 ± 2 days).

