Subjects who meet the above criteria will be considered discontinued from dosing. However, the investigator may ask the subject to continue their participation in the study, so they can be monitored for safety and PK, or the investigator may withdraw the subject from the trial.

9.4.3 *Replacement of withdrawn subjects*

Withdrawn subjects will be replaced at the discretion of the sponsor and investigator. Subjects withdrawn because of AEs considered possibly related to study treatment (see section 14.2) will not be replaced. Replacements for other withdrawn subjects will receive the treatments intended for the withdrawn subject, from the start of the trial. For subjects in Part B, the sponsor and investigator will decide which sessions the replacement subject will complete.

10 *Treatments*

10.1 *Treatments administered*

In Part A, subjects will receive a single oral dose of BEN8744 or placebo.

In Part B, subjects will receive a single oral dose of BEN8744 on 2 different occasions, separated by a washout of at least 7 days.

In Part C, subjects will receive once or twice-daily oral doses of BEN8744 or placebo for 14 days.

Fasting requirements are described in section 11.

All treatments will be administered orally with approximately 240 mL of water. All treatments will be given in the fasted state in Parts A, and in the fasted or fed state in Part C.

10.2 *Overdose*

Symptoms of overdose of BEN8744 are not yet known. In the case of accidental overdose, subjects should be treated symptomatically as no specific antidote is available.

10.3 *Blinding (Parts A and C only)*

The trial medication will be repackaged and relabelled by the HMR Pharmacy, according to the randomisation schedule. Active and placebo treatments will be labelled such that it is not possible to distinguish between them. If the expiry dates of placebo and active treatment differ, both treatments will be labelled with an expiry

date no later than the earlier of the 2 expiry dates. Each subject's treatment will be given a unique code number, traceable to the batch number of the medication.

The placebo and active treatments for each group will be identical in appearance, and similar in taste and smell. To maintain the blind nature of the trial, the same number of capsules will be given to each subject in a group.

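### The Part B food-effect ANOVA names no subject, period or sequence term, so the 90% CI for fed:fasted carries between-subject variance and is likely to be too wide

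*Combined protocol and SAP*

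**What the plan says.** Section 2.4 describes the design: "Part B will test the effect of food on the PK of BEN8744 in an open-label, randomised, 2-way crossover design". Section 8.1.2 adds that "the order will be randomised 1:1, as shown in Table 7", and Table 7 puts three subjects in each sequence of a group of six.

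The analysis is in section 16.2.7 under the food-effect heading. ANOVA models are fitted with log AUCinf, AUClast and Cmax "as the dependent variables, and formulation as a fixed effect". Least-squares means and the residual variance from that model give the 90% CI for fed against fasted. The decision rule is: "Food effect will be concluded if the 90% CI of the ratio (fed:fasted) is not included within the range 80–125" (per cent). For tmax, a Hodges-Lehmann estimate is planned and "the 90% CI generated with the Moses method will be presented".

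Section 6.2.4 reports from Cohorts A1–A4: "Additionally, between-subject variation was high". On replacements, section 9.4.3 says: "For subjects in Part B, the sponsor and investigator will decide which sessions the replacement subject will complete". Section 16.2.1 says a separate SAP will be written before database lock. Section 16.3 gives no sample-size basis.

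**The concern.** A crossover gains its precision by comparing each subject with himself or herself. That requires the model to remove the subject effect. The only term named here is 'formulation', which in Part B can only mean food condition. With that term alone, the 12 values in a group are analysed as two independent samples of six, and the residual holds between-subject plus within-subject variance.

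This is the stated analysis of Part B's primary objective. The interval labelled 90% would not have 90% coverage. Because a food effect is concluded unless the whole interval lies inside 80–125%, extra width pushes towards declaring one that is not there.

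Three smaller faults sit in the same paragraph:
- Fed and fasted are conditions, not formulations, and the product is a capsule (section 13.1), not a solution.
- The tmax sentence does not say whether the estimate uses within-subject differences, period differences compared between sequences, or unpaired values. The Moses interval is a two-independent-sample method.
- Period is omitted. That does not bias the ratio with complete 3:3 data, but it can if subjects drop out or a replacement completes only one session.

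**Working it through.** The plan states no power, error rate or expected CI width for Part B, so there is no figure to reproduce. The check compares the interval as written with the standard crossover interval.

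**Total SD on the log scale.** From the Table 2 ranges (six subjects per dose), SD ≈ ln(max/min)/2.534, where 2.534 is the expected range of six standard normal values.

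| Dose | AUCinf range | log-SD | Cmax range | log-SD |
|---|---|---|---|---|
| 6 mg | 5.67–26.4 | 0.61 | 1.33–11.30 | 0.84 |
| 20 mg | 77.3–210 | 0.39 | 20.7–57.7 | 0.40 |
| 60 mg | 494–2,390 | 0.62 | 130–688 | 0.66 |

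Section 8.1.2 states that "the dose selected for Group B1 will be no higher than 50% of the highest dose tested in Part A" that caused no safety concerns. That is at most 30 mg from the completed 60 mg cohort, or 50 mg if 100 mg qualifies. The 20 mg spread is therefore at least as relevant as the 60 mg spread, and totals of 0.40 and 0.62 are both carried forward.

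**Within-subject SD.** This is not in the documents. It is assumed and varied.

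**Half-width of the 90% CI on the log scale, n = 6.**
- As written (10 df): 1.812 × s_total × √(2/6)
- Crossover model (4 df): 2.132 × s_within × √(2/6)

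Putting in the true SDs at a point ratio of 1.0:
- As written, total 0.40: 1.812 × 0.577 × 0.40 = 0.419, so 0.66–1.52.
- As written, total 0.62: 0.649, so 0.52–1.91.
- Crossover, within-subject SD 0.25: 2.132 × 0.577 × 0.25 = 0.308, so 0.74–1.36.

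**Simulation.** 400,000 trials per scenario, 3:3, log-normal with a subject effect and no period effect. Median half-widths are slightly narrower than the plug-in values because the median estimated SD lies below the true one. At within-subject SD 0.25 the median intervals are 0.67–1.49 (total 0.40) and 0.54–1.84 (total 0.62) as written, against 0.75–1.33 with the crossover model.

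| Within-subject SD | Width ratio, total 0.40 | Coverage as written, 0.40 | Width ratio, total 0.62 | Coverage as written, 0.62 |
|---|---|---|---|---|
| 0.20 | 1.75 | 99.2% | 2.70 | 99.9% |
| 0.25 | 1.41 | 98.0% | 2.16 | 99.7% |
| 0.30 | 1.18 | 96.1% | 1.81 | 99.3% |

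The crossover model covers 90% throughout.

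**Decision rule, true ratio 1.0: share of trials concluding a food effect.**

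| Within-subject SD | As written, total 0.40 | As written, total 0.62 | Crossover model |
|---|---|---|---|
| 0.15 | 98.6% | 99.8% | 57% |
| 0.20 | 99.2% | 99.9% | 82% |
| 0.25 | 99.6% | over 99.9% | 92% |
| 0.30 | 99.8% | over 99.9% | 96% |

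At a true ratio of 1.5, a food effect is concluded in over 99.6% of trials under either model.

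**Largest residual SD that still fits 80–125% at a point ratio of 1.00.**
- As written: ln(1.25)/(1.812 × 0.577) = 0.213, applied to the total SD.
- Crossover: ln(1.25)/(2.132 × 0.577) = 0.181, applied to the within-subject SD.

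All six total log-SDs from Table 2 (0.39–0.84) exceed 0.213.

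**Where the widening stops.** The model as written has more degrees of freedom, so it loses only if subjects' fed and fasted values are correlated. With plug-in SDs, break-even is at total/within = 2.132/1.812 = 1.18, a correlation of 1 − 1/1.18² ≈ 0.28. By median width it is about 0.2. At zero correlation the interval as written is slightly narrower (ratio 0.90).

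**The case against.** The strongest reply is that the sentence is incomplete, not wrong. It does not say that food condition is the only term, least-squares means are the language of multi-term models, and the crossover is stated elsewhere. The SAP, still to come, may well give the full model. An unpaired analysis was possibly never intended. But the protocol is the only specification available, it names one term, and it builds the interval from that model's residual. An unwritten SAP does not repair that.

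Second, most of the false conclusions come from applying 80–125% to six subjects. At within-subject SDs of 0.20, 0.25 and 0.30 with total SD 0.40, the model adds about 17, 8 and 4 percentage points to what the correct analysis would give anyway. The large contrast needs a within-subject SD of 0.15, which nothing in the documents supports. This stands: the excess width and coverage are the firmer consequence, and the effect on the rule is secondary.

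Third, the inputs are thin. Sampling error on a six-subject range puts the 20 mg AUCinf SD (0.394) anywhere from roughly 0.23 to 0.94, and the 60 mg value (0.622) from 0.36 to 1.48. Section 6.2.4 describes gut efflux and metabolism effects at lower doses, so low within-subject variability cannot be presumed. At total SD 0.40 the width ratio falls to 1.02 at within-subject SD 0.35 and 0.92 at 0.39. This stands as a limit on size.

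Fourth, the stakes are moderate. Section 16.2.2 calls the trial exploratory, the error is towards declaring a food effect, and the Safety Review Group makes fed/fasted choices on the available data, not by this interval alone.

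**Conclusion.** The concern holds. As written, the model does not fit the design, and the nominal 90% interval over-covers whenever fed and fasted values within a subject are more than weakly correlated (above about 0.2 to 0.3). With within-subject log-SD assumed at 0.20–0.30, the interval is about 1.2 to 1.75 times too wide at a total SD of 0.40 and 1.8 to 2.7 times too wide at 0.62. Figures beyond the first digit should not be leaned on, since the total SDs come from six-subject ranges and the within-subject SD is assumed.

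The ratio is unbiased in complete 3:3 data, and a real food effect of the size examined is not missed. Correcting the model restores coverage and precision but does not make the 80–125% rule workable with six subjects. This should be fixed before the SAP is finalised; it does not threaten the trial.

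**What to change.** Replace the model sentence in section 16.2.7, and carry the same text into the SAP:

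- Log AUCinf, AUClast and Cmax are analysed in a mixed model with fixed effects for food condition (fed/fasted), period and sequence, and subject within sequence as a random effect. The 90% CI for fed:fasted comes from the within-subject residual. Fixed or random subject effects give the same interval in complete data (4 df); a small-sample df method should be named for incomplete data.
- Replace 'formulation' and 'solutions' with food condition.
- For tmax, compare period differences between sequences, which is compatible with the Moses interval. If paired within-subject differences are preferred, name a paired interval in place of Moses.
- State that with six subjects the 80–125% rule will often fail even with no food effect, so the ratio and its CI carry the interpretation.
- Say how the model applies to optional Group B2, which may use another dose or meal.

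The cost is protocol and SAP wording. No extra subjects, samples or data are needed.

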A linear non-parametric superposition approach was used to predict drug concentrations after single or multiple dosing using Phoenix WinNonlin® Version 8.4. Predicted drug concentrations at 100 and 140 mg QD, and 50 mg BID, were based on both mean plasma concentration profiles and the individual plasma profile of the subject with the highest exposure to date (Cohort A4 [60 mg]).

Table 2: Summary of (mean [range]) actual and predicted (100 and 140 mg) BEN8744 plasma PK parameters after single oral doses of 2–60 mg in healthy subjects

Dose (mg)	N	Mean (range)			
		C_{\max} (ng/mL)	t_{\max}^a (h)	AUC_{24} (ng*h/mL)	AUC_{inf} (ng*h/mL)
2 ^b	6	1.34 (0.59–2.68)	2.00 (2.00–2.00)	–	–
6	6	5.03 (1.33–11.30)	1.50 (0.50–3.00)	15.23 (5.68–26.6)	15.16 (5.67–26.4)
20	6	46.1 (20.7–57.7)	2.00 (1.00–3.00)	163.25 (77.40–210)	164.12 (77.30–210)
60	6	352.83 (130–688)	1.00 (1.00–2.00)	1,057.27 (494–2,380)	1,059.2 (494–2,390)
100 pred ^c	–	1,100	1.35	3,950	3,986
140 pred ^c	–	1,541	1.35	5,530	5,581

[figure not shown]
SD = standard deviation; C_{\max} = maximum plasma concentration; t_{\max} = time of C_{\max} ; AUC_{24} = area under the concentration–time curve from time zero to time 24 h; AUC_{inf} = area under the concentration–time curve extrapolated to infinite time; pred: predicted; max: maximum.

^a Median (min – max).

^b Insufficient plasma concentration data at terminal phase to estimate terminal phase related pk parameters.

^c 100 mg and 140 mg profiles predicted based on the individual plasma profile of the subject with the highest exposure to date (Cohort A4 [60 mg]), using a nonparametric superposition function.

Figure 2: Mean (SD) BEN8744 plasma concentration–time profiles after single oral doses of 2–60 mg (observed) and 100 mg (individual predicted) in healthy subjects (linear and semilogarithmic scale)

SD = standard deviation; IC50/90 = concentration required for 50%/90% inhibition.

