7.1 Objectives

7.1.1 Primary objectives

Part A: To assess the safety and tolerability of single ascending oral doses of BEN8744 in healthy subjects

Part B: To characterise the effect of food on the pharmacokinetic (PK) profile of at least 1 dose of BEN8744

Part C: To assess the safety and tolerability of multiple ascending oral doses of BEN8744 in healthy subjects

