16.2.2 Statistical hypotheses

The trial is an exploratory one, and there are no null hypotheses to be tested.

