16.3 Determination of sample size

Since this is a Phase 1 study, no formal sample size determination is appropriate.

17 Ethical and regulatory requirements

The trial proposal will be reviewed by a recognised REC, and by the MHRA. The trial will not proceed unless the sponsor obtains from the MHRA a clinical trial authorisation (CTA), and the REC approves the trial.

The trial will be done at HMR, in compliance with The Medicines for Human Use (Clinical Trials) Regulations 2004 and current amendments⁴², The Medicines for Human Use (Clinical Trials) (Amendment) (EU Exit) Regulations 2019⁴³, The Human Medicines (Amendment etc) (EU Exit) Regulations of 2019 and 2020^{44,45}, GMP³⁷, the SOPs issued by RES for RECs in the UK³⁸, and Good Clinical Practice, which has its origins in the Declaration of Helsinki.

All subjects must give written consent to participate in this trial. Consent for screening evaluations may be obtained using the information and consent form for the HMR healthy volunteer panel, which has been approved by the Health Research Authority's Generic Review Committee. The trial-specific information and consent form will be signed by the subject either before any screening evaluation or after the investigator confirms the eligibility of the subject for the trial and before the subject is randomised to receive the first administration of IMP. Before giving consent, subjects must read the information sheet about the trial. They must also read the consent form. They will then discuss the trial with the investigator or his deputy and be given the opportunity to ask questions. The trial-specific information sheet and the consent form must be approved by the REC.

Each subject is free to withdraw from the trial at any time, without giving a reason. If a subject withdraws, the investigator will ask the subject to consent to a follow-up examination. For withdrawn subjects, the investigator will use a special information and consent form which has been ethically approved. If the subject consents to the

follow-up examination but asks the investigator to destroy all identifiable samples taken from the subject and/or not enter into the eCRF results of the follow-up examination, the investigator will comply with the subject's requests.

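### The Part B rule declares a food effect whenever absence of one has not been shown; with 6 subjects and no true effect, that is wrong in more than half of trials once within-subject CV exceeds about 14%

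*Combined protocol and SAP*

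**What the plan says.** Section 7.1.1 gives the Part B primary objective: "Part B: To characterise the effect of food on the pharmacokinetic (PK) profile of at least 1 dose of BEN8744". Table 7 in section 8.1.2 sets the size of each comparison, "Treatment sequence for each group (n=6 each) in Part B", with three subjects per sequence. A second group does not enlarge the first: "Group B2 is optional and may be required if the Sponsor decides to test the effect of food at an additional dose level". Its other stated use is to try a different meal or fasting requirement.

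Section 16.2.7 fits ANOVA models to log AUCinf, log AUClast and log Cmax, with formulation as the only named effect. "The estimated least square means and residual variance from the model will be used to construct 90% CIs" for fed versus fasted. The decision rule follows: "Food effect will be concluded if the 90% CI of the ratio (fed:fasted) is not included within the range 80–125" per cent.

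Section 16.2.2 says "The trial is an exploratory one, and there are no null hypotheses to be tested", and section 16.3 says "no formal sample size determination is appropriate". No within-subject CV, expected ratio or target precision is given for Part B.

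**The concern.** A 90% CI inside 80–125% is the usual evidence that two conditions do not differ materially. A CI that is not inside the range can arise in two ways: the ratio really is far from 1, or the interval is too wide to tell. The rule treats both as a demonstrated food effect. It does not require the CI to exclude 100%, and it does not require the point estimate to lie outside 80–125%. A ratio of exactly 100% with a CI of 78–128% would have to be reported as a food effect.

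With 6 subjects, wide intervals are likely, and nothing in the plan sized the group to avoid them. The rule also speaks of one ratio although three parameters are modelled, so it does not say whether one failing parameter or all three trigger the conclusion.

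At stake is the stated conclusion on Part B's primary objective.

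**Working it through.** The plan states no power, CV or derived sample size for Part B, so there is no figure of its own to reproduce.

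**Inputs from the documents**
- n = 6 per comparison, two-way crossover, 3 per sequence (section 8.1.2, Table 7).
- 90% CI on the log scale, limits 0.80 and 1.25 (section 16.2.7).

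**Assumptions**
- True fed:fasted ratio 1.00, one parameter.
- Standard 2×2 crossover analysis, so residual df = n − 2 = 4 and t(0.95, 4) = 2.132. Section 16.2.7 does not name subject, period or sequence terms.
- Within-subject SD on the log scale (s) from 0.08 to 0.40, where CV = √(exp(s²) − 1).

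**Width of the interval**

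The standard error of the log ratio is s × √(2/6), so the CI half-width is 2.132 × ŝ × 0.5774, where ŝ is the estimated SD. At a point ratio of exactly 1.00 the CI fits inside 80–125% only if

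ŝ ≤ ln(1.25) / (2.132 × 0.5774) = 0.2231 / 1.2308 = 0.181.

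- At ŝ = 0.20 the half-width is 0.246 and the CI is 0.78–1.28.
- At ŝ = 0.30 the half-width is 0.369 and the CI is 0.69–1.45.

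**Probability of a wrong conclusion**

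The log ratio is normal with mean 0 and SD s√(2/6), and 4ŝ²/s² is chi-square with 4 df, independently. Integrating over both gives the probability that the CI is not contained in 0.80–1.25 when food has no effect:

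| Within-subject SD | P(food effect concluded, true ratio 1.00) |
|---|---|
| 0.08 | 2.6% |
| 0.10 | 13.4% |
| 0.15 | 56.5% |
| 0.20 | 81.7% |
| 0.25 | 92.0% |
| 0.30 | 96.2% |
| 0.40 | 99.0% |

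The rate reaches 50% at SD 0.142 (CV 14.2%) and 80% at SD 0.195 (CV 19.7%). A paired analysis with 5 df moves the 50% point only to CV 14.7%.

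**How many of these are merely wide intervals**

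Simulation at SD 0.20 shows the CI excluding 100% in 10% of null trials, as a 90% CI should. In 73% of all null trials the CI contains 100% and the rule still declares a food effect.

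**Subjects needed for the rule to behave**

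The smallest even n that holds the wrong conclusion to 20% or less (df = n − 2) is 10, 16, 24 or 34 at SD 0.15, 0.20, 0.25 or 0.30, against 6 planned.

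**More than one parameter**

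If failure on any one parameter triggers the conclusion, the error is higher. With two independent parameters at CV 12%, the single-parameter rate of 30.5% becomes 1 − (1 − 0.305)² = 52%. Two AUCs and Cmax from the same subjects are correlated, so this is an illustration only.

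**The model as literally written**

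With formulation as the only term, between-subject variance enters the residual (df 10). Converting the AUCinf ranges in Table 2 to SDs (range divisor 2.534 for n = 6):
- 20 mg: ln(210/77.30)/2.534 = 0.39
- 60 mg: ln(2,390/494)/2.534 = 0.62

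Simulated wrong-conclusion rates for within-subject SD 0.05–0.30 are then 94.5–99.7% and 99.3–99.98%. Much of that comes from the missing subject term, which is a separate matter. The rates in the table above do not rely on it.

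**The case against.** The strongest case against is that little depends on the label. The fed:fasted ratios and 90% CIs are reported whatever the rule says, and they meet an objective worded as characterising the effect. Section 8.5.4 has the Safety Review Group choose fed or fasted dosing in Part C from the available safety, tolerability and PK data, and nothing shows it relying on this conclusion. The trial is declared exploratory, and section 16.2.1 says a statistical analysis plan will be written before database lock. The 14% threshold also rests on a CV the documents do not give, a true ratio of exactly 1.00, and a crossover model with 4 df that section 16.2.7 does not spell out. Below that CV the rule is right in most null trials.

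Much of this stands. The estimates are unharmed, no effect on Part C is shown, and the error rate is conditional on its assumptions. A per-parameter reading of the singular ratio is also natural, since the models are fitted per parameter.

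It does not rescue the sentence. The misreading of a wide interval is a matter of logic and holds at any CV; the CV determines only how often it bites. The protocol states the rule outright, so a later plan that follows it inherits the error. The exploratory status argues for reporting estimates, not for a default positive verdict.

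**Conclusion.** The concern holds. As written, section 16.2.7 turns failure to show absence of a food effect into a conclusion that food has an effect, and no other section supplies an inconclusive outcome. With 6 subjects, a standard crossover analysis and a true ratio of 1.00, that conclusion is wrong for a single parameter in more than half of trials once within-subject CV exceeds about 14%, and in about four-fifths at a CV near 20%. The within-subject CV is assumed throughout. If it is as low as 8%, the rule seldom misfires. The defect is confined to the prespecified conclusion on Part B's primary objective and should be corrected before the data are analysed.

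**What to change.** Replace the sentence in section 16.2.7 with wording such as: *Absence of a food effect will be concluded if the 90% CIs of the fed:fasted ratios for AUCinf, AUClast and Cmax all lie wholly within 80–125%; otherwise absence of a food effect is not established, and the ratios with their 90% CIs will be reported as estimates.* This also settles how the three parameters combine. Alternatively, delete the rule and report estimates only, which fits sections 16.2.2 and 16.3. The statistical analysis plan should carry the same wording.

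A rule for positively concluding a food effect is not needed. If the sponsor wants one, its operating characteristics should be worked out first. For example, requiring the CI to exclude 100% and the point estimate to lie outside 80–125% would detect a true ratio of 1.30 in only about 51% of trials at SD 0.20 with 6 subjects.

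The cost is one sentence before database lock, with no change to data, sample size or estimates. The price is candour: at n = 6 the report will often have to say that absence is not established. At SD 0.20 this happens in 82% of null trials for a single parameter, and in more when all three must pass.
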